**Difference in pooled incidence rates [patient/100 patient – years]**

$$= 100 \times \left\{ \frac{\sum \left( \frac{a_i PT_{0i} - b_i PT_{1i}}{T_i} \right)}{\sum \left( \frac{PT_{1i} PT_{0i}}{T_i} \right)} \right\}$$

95% confidence interval for difference in pooled incidence rates [patient/100 patient – years]

$$= 100 \times \left\{ \frac{\sum \left( \frac{a_i PT_{0i} - b_i PT_{1i}}{T_i} \right)}{\sum \left( \frac{PT_{1i} PT_{0i}}{T_i} \right)} \pm 97.5 \text{ percentile for standard normal distribution} \right. \\ \left. \times \sqrt{\frac{\sum \left( \frac{PT_{1i} PT_{0i}}{T_i} \right)^2 \left( \frac{a_i}{PT_{1i}^2} + \frac{b_i}{PT_{0i}^2} \right)}{\left( \sum \frac{PT_{1i} PT_{0i}}{T_i} \right)^2}} \right\}$$

- Ratio of pooled incidence proportions between treatment groups and its 95% confidence interval

$$\text{Ratio of pooled incidence proportions} = \frac{\sum \left( \frac{a_i N_{0i}}{S_i} \right)}{\sum \left( \frac{b_i N_{1i}}{S_i} \right)}$$

95% confidence interval for ratio of pooled incidence proportions

$$= \exp \left\{ \ln \left[ \frac{\sum \left( \frac{a_i N_{0i}}{S_i} \right)}{\sum \left( \frac{b_i N_{1i}}{S_i} \right)} \right] \pm 97.5 \text{ percentile for standard normal distribution} \right. \\ \left. \times \sqrt{\frac{\sum \left( \frac{M_{1i} N_{1i} N_{0i}}{S_i^2} - \frac{a_i b_i}{S_i} \right)}{\left( \sum \frac{a_i N_{0i}}{S_i} \right) \left( \sum \frac{b_i N_{1i}}{S_i} \right)}} \right\}$$

Xeljanz group

$a_i$ : Number of patients with the event in Stratum i [patient]

$N_{1i}$ : Number of patients in Stratum i [patient]

Control group

$b_i$ : Number of patients with the event in Stratum i [patient]

$N_{0i}$ : Number of patients in Stratum  $i$  [patient],

$$M_{1i} = a_i + b_i$$

$$S_i = N_{1i} + N_i$$

- Difference in pooled incidence proportion between the treatment groups and the 95% confidence interval

$$\text{Difference in pooled incidence proportion [%]} = 100 \times \frac{\sum \left( \frac{a_i N_{0i} - b_i N_{1i}}{S_i} \right)}{\sum \left( \frac{N_{1i} N_{0i}}{S_i} \right)}$$

95% confidence interval for the difference in pooled incidence proportion [%]

$$= 100$$

$$\times \left[ \frac{\sum \left( \frac{a_i N_{0i} - b_i N_{1i}}{S_i} \right)}{\sum \left( \frac{N_{1i} N_{0i}}{S_i} \right)} \pm 97.5 \text{ percentile for standard normal distribution} \right]$$

$$\times \sqrt{\frac{\sum \left( \frac{a_i N_{0i} - b_i N_{1i}}{S_i} \right)}{\sum \left( \frac{N_{1i} N_{0i}}{S_i} \right)} \sum U_i + \sum V_i}$$

$$U_i = \frac{N_{1i}^2 b_i - N_{0i}^2 a_i + N_{1i} N_{0i} (N_{0i} - N_{1i})/2}{S_i^2}$$

$$V_i = \frac{a_i (N_{0i} - b_i) + b_i (N_{1i} - a_i)}{2S_i}$$

- Adjusted hazard ratio and the 95% confidence interval

The hazard ratio adjusted for covariates and the 95% confidence interval will be estimated using a Cox proportional hazard model.

In addition, the proportional hazard assumption will be confirmed using the log-log plots of Kaplan-Meier estimates.

- **Propensity scores**

Propensity scores will be calculated by a logistic regression analysis and random forests using treatment groups as an objective variable and covariates described in “6.3 Covariates” as an explanatory variable. If candidate covariates (6.3) are missing (including unknown), they will be complemented by multiple imputation. The number of the datasets will be determined depending on a situation of the missing. This analysis is conducted by each dataset and the estimate is obtained by the integrated results

- **Analysis by multiple imputation method**

Missing data (including unknown) of covariates are complemented from variables with a small number of missing data by random forests using a fully conditional specification (FCS) algorithm as a multiple imputation method. The number of data sets to be complemented and created by the multiple imputation method is determined according to the rate of missing data. After complementation, analysis is performed for each created data set. The average value of the analysis results obtained for each data set is used as the point estimation value by the multiple imputation method. The point estimate and variance are calculated as follows.

$$\text{Point estimate } \bar{\theta}_M = \frac{1}{M} \sum_{m=1}^M \bar{\theta}_m$$

$$\text{Variance } T_M = \bar{W}_M + \left(1 + \frac{1}{M}\right) \bar{B}_M$$

$$\bar{W}_M = \frac{1}{M} \sum_{m=1}^M \text{var}(\bar{\theta}_m), \quad \bar{B}_M = \frac{1}{M-1} \sum_{m=1}^M (\bar{\theta}_m - \bar{\theta}_M)^2$$

- **Standardized incidence ratio (SIR) and the 95% confidence interval**

$$\text{SIR [%]} = \frac{\sum_{ij} d_{ij}}{\sum_{ij} p y_{ij} \lambda_{ij}} = \frac{D}{E}$$

Sex and age class	Reference population			Control population	
	Population	Number of patients	Incidence Rate	Duration of exposure	Number of patients
ij	N ij	n ij	$\lambda_{ij}$ (=n ij /N ij )	p y ij	d ij

$$SIR(SMR) = \frac{\sum_{ijk} d_{ijk}}{\sum_{ijk} p y_{ijk} \lambda_{ijk}} = \frac{D}{E}$$

Sex, age class and calendar year	Reference population			Control population	
	Population	Number of patients	Incidence Rate	Duration of exposure	Number of patients (deaths)
ijk	$N_{ijk}$	$n_{ijk}$	$\lambda_{ijk}$ ( $= n_{ijk}/N_{ijk}$ )	$py_{ijk}$	$d_{ijk}$

Lower limit of 95% confidence interval of standardized incidence ratio =  $\frac{\chi^2_{2D,0.025}}{2E}$

Upper limit of 95% confidence interval of standardized incidence ratio =  $\frac{\chi^2_{2(D+1),0.975}}{2E}$

$\chi^2_{v,\alpha}$ : Alpha percent point in chi-square distribution with  $v$  degrees of freedom

## 8.2. Statistical Analysis

### 8.2.1. Summary of Patients

- Composition of patients

In registered patients, the number of registered patients, patients for whom the CRF is collected, patients included in the safety analysis, and patients included in the efficacy analysis will be calculated. In addition, the number of patients for whom the CRF is not collected, patients excluded from the safety analysis, and patients excluded from the efficacy analysis, and the number of patients by reason for exclusion will be calculated.

In patients included in the safety analysis in the Xeljanz group, the number of patients who meet the MTX criteria will be calculated. In addition, the number of patients who do not meet the MTX criteria and the number of patients by reason for exclusion will be calculated.

- Status of discontinuation and dropout

In the safety and efficacy analysis sets, the number and proportion of patients who discontinued administration of Xeljanz and follow-up in the Xeljanz group and the number of patients by reason for discontinuation will be calculated for each of the number of days to discontinuation shown in Table 2.

The number and proportion of patients who discontinued the survey and follow-up in the control group and the number of patients by reason for discontinuation will be calculated.

Time to discontinuation of administration of Xeljanz in the Xeljanz group and time to discontinuation of the survey in the control group will be summarized in accordance with **Section 8.1.4.** The censoring period in patients without discontinuation will be the newest date of completion of administration.

**Table 2. Categories of Tabulation Items for Discontinuation and Dropout**

Item	Category
Reason for discontinuation	Remission (Xeljanz group only), inadequate clinical effect (Xeljanz group only), adverse events (Xeljanz group only), death of patient, no revisits, transfer to other hospitals and departments, administration of Xeljanz Tablets (survey the control group only), others
Number of days to discontinuation	Start of treatment - 1 month (Day 1 to Day 31), 1 month < - 3 months (Day 32 to Day 92), 3 months < - 6 months (Day 93 to Day 184), 6 months < - 9 months (Day 185 to Day 275), 9 months < - 12 months (Day 276 to Day 366), 12 months < - 18 months (Day 367 to Day 549), 18 months < - 24 months (Day 550 to Day 731), 24 months < - 30 months (Day 732 to Day 914), 30 months < - 36 months (Day 914 to Day 1096), >36 months (Day 1097-)

- Lists of excluded patients**

Patients excluded from the safety analysis set, patients excluded from the subpopulation that meets the MTX criteria, patients excluded from the efficacy analysis set, and reasons for exclusion will be listed.

#### **8.2.2. Analysis of Patient Background and Treatment History**

- Distribution and summary statistics of patient background**

In the safety and efficacy analysis sets, the frequency of patient background will be calculated. Summary statistics will be calculated for continuous data.

In each of the safety and efficacy analysis sets, the calculation will also be made for new patients whose treatment started from this survey, patients who participated in clinical trials, and patients transferring from other hospital. Furthermore, in new patients, the calculation will also be made for the subpopulations that do and do not meet the MTX criteria in the Xeljanz group.

Items for which the calculation will be made are shown in “[Appendix 11.1.2 Patient Background](#).”

- Status of the implementation of tests**

In the safety analysis set in the Xeljanz group, the number and proportion of patients with tests before the initiation of administration of Xeljanz shown in [Table 3](#) will be calculated for each test timing.

The number and proportion of patients with no test prior to the start of study treatment, and with a test performed after the start of study treatment (Day 2 onward) will be calculated.

**Table 3. Categories of Tabulation Items for the Status of the Implementation of Tests**

Item	Category
Test	Test (implemented if at least one is met), chest X-ray or chest CT (chest X-ray, chest CT), interferon $\gamma$ or tuberculin reaction (interferon $\gamma$ , tuberculin reaction), hepatitis B and C virus test (HBs antigen, HBs antibody, HBc antibody, HBV-DNA test, HCV antibody)
Test timing	after the initiation of administration of Xeljanz (Day 2-), before the initiation of administration of Xeljanz $\leq$ 3 months (Day -30 to Day 0), before the initiation of administration of Xeljanz $>$ 3 months (-Day 31), before the initiation of administration of Xeljanz $>$ 3 months to $\leq$ 6 months (Day -183 to Day -31), before the initiation of administration of Xeljanz $>$ 6 months to $\leq$ 12 months (Day -364 to Day -182), before the initiation of administration of Xeljanz $>$ 12 months to $\leq$ 24 months (Day -729 to Day -365), before the initiation of administration of Xeljanz $>$ 24 months (-Day -730)

- Past medical histories**

In the safety analysis set, the number and proportion of patients with past medical histories will be calculated for each system organ class (SOC) and preferred term (PT).

- Complications**

In the safety analysis set, the number and proportion of patients with complications (current medical history) will be calculated for each SOC and PT.

- Concomitant drugs**

In the safety and efficacy analysis sets in the Xeljanz group, the number and proportion of patients who used concomitant drugs will be calculated. A biological therapeutic or immunosuppressant terminated on the same day as the first dose of Xeljanz or started on the same day as the last dose of Xeljanz will not be considered as a concomitant drug.

Similarly, the number and the proportion of patients will be calculated by methotrexate (MTX), biological agents, DMARDs and immunosuppressive agents other than MTX, oral steroids and other drugs.

- Non-drug therapies**

In the safety and efficacy analysis sets in the Xeljanz group, the number and proportion of patients who underwent surgical therapies for rheumatoid arthritis (surgery scheduled before the initiation of this survey) will be calculated.

- **Prior medications**

In the safety and efficacy analysis sets, the number and proportion of patients who used each prior medication will be calculated. A biological therapeutic or immunosuppressant terminated on the same day as the first dose of Xeljanz will be considered as a prior medication.

Similarly, the number and the proportion of patients will be calculated by methotrexate (MTX), biological agents, DMARDs and immunosuppressive agents other than MTX, oral steroids and other drugs.

- **Status of administration**

The following variables will be calculated for the safety analysis set of Xeljanz group: Daily number of administrations at the first time, initial daily dose, duration of administration, overall administration period, duration of each administration, duration of actual administration, total number of administrations, total dose, average daily number of administrations, average daily dose, average daily number of actual administrations, and average actual daily dose.

Daily number of administrations at the first time [time] = daily number of administrations recorded in the administration status for the oldest initiation date

Initial daily dose [mg] =  $5 * \text{Daily number of administrations at the first time}$   
Duration of administration [day] = newest completion date - oldest initiation date + 1

Overall administration period [patient-year] = Administration period including drug cessation periods / 365.25

Duration of each administration [day] = completion date - initiation date + 1

Duration of actual administration [day] = sum of the duration of each administration (not including drug cessation periods)

Total number of administrations [time] = product of each daily number of administrations and the duration of each administration

Total dose [mg] =  $5 * \text{Total number of administrations}$

Average daily number of administrations [time/day] = total number of administrations/duration of administration

Average daily dose [mg] =  $5 * \text{Average daily number of administrations}$

Average daily number of actual administrations [time/day] = total number of administrations/duration of actual administration

Average actual daily dose [mg] = 5\*Average daily number of actual administrations

Continuous data will be summarized in accordance with [Section 8.1.1](#). Categorical data shown in [Table 4](#) will be summarized in accordance with [Section 8.1.2](#).

In addition, as a method to allow more detailed understanding of the daily number of administrations, the distribution ratio of the daily number of administrations (once, twice,  $\geq 3$  times, unknown) during the duration of actual administration in each patient will be calculated in percentage (%) (eg; once, 10%; twice, 85%; and  $\geq 3$  times, 5%). For the distribution ratio of each daily number of administrations, frequency and the proportion will be calculated by category ( $\leq 20\%$ ,  $>20\%$  to  $\leq 40\%$ ,  $>40\%$  to  $\leq 60\%$ ,  $>60\%$  to  $\leq 80\%$ , and  $>80\%$  to  $\leq 100\%$ ).

The initial drug used for treatment will be tabulated for the safety analysis set of the control group. Also, the number and proportion of patients in each assessment period who are receiving the same drug as the initial drug will be calculated.

For each assessment timepoint, comply with the target dates specified in "[Appendix 11.1.1 Definition of Visit Timing](#)".

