#### (2) Pre-treatment observation

##### [8] Contraindication (presence/absence of contraindication)

##### [9] Tuberculosis check (imaging diagnosis/tuberculin test/interferon $\gamma$ measurement (Quantiferon test, T-SPOT test, etc.)/antituberculosis drug administration)

The results of tests within 3 months prior to the start of treatment should be recorded before the treatment.

\*Patients with concurrent or suspected tuberculosis should be given appropriate antituberculosis drug.

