##### [10] Hepatitis B virus test (HBs antigen, HBs antibody, and HBc antibody)

The results of tests within 3 months prior to the start of treatment should be recorded.

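### SAP Table 3 gives its class for tests up to 3 months before start a one-month day range, leaves the start day without a timing class, and puts two days in two classes

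*SAP*

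**What the plan says.** SAP Section 8.2.2 tabulates, for the safety analysis set of the Xeljanz group, how many patients had chest X-ray or CT, interferon gamma or tuberculin tests, and hepatitis B and C tests, by timing class. Table 3 defines the classes by a label in months and a day range in brackets:

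- At most 3 months before start: "3 months (Day -30 to Day 0".
- More than 3 months before start: "3 months (-Day 31". The oldest class in the same table is printed as running up to Day -730, so this one is read as up to Day -31, with a minus sign lost.
- More than 3 and at most 6 months: "6 months (Day -183 to Day -31".
- More than 6 and at most 12 months: "12 months (Day -364 to Day -182".
- More than 12 and at most 24 months: Day -729 to Day -365. More than 24 months: Day -730 and earlier.
- Post-start tests: "after the initiation of administration of Xeljanz (Day 2" and later.

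Appendix 11.1.1 makes Day 1 the first administration date and numbers days as assessment date minus Day 1 date plus 1.

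Protocol 7.1 sets a 3-month window for two registration items. For the tuberculosis check: "The results of tests within 3 months prior to the start of treatment should be recorded before the treatment". For HBs antigen, HBs antibody and HBc antibody: "The results of tests within 3 months prior to the start of treatment should be recorded".

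**The concern.** The label and the day range of the first class contradict each other: Day -30 is about one month before start. The error carries into the next classes, because both the total class beyond 3 months and the 3-to-6-month class begin at Day -31. Two further faults appear at the other boundaries. The start day lies between the last day counted as before (Day 0) and the first day counted as after (Day 2). The 3-to-6-month and 6-to-12-month classes overlap.

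Table 3 shows how recent the screening tests were, in a survey whose main safety concerns include serious infection. A programmer who follows the printed ranges would report recent tests as old ones, and a reader would conclude that fewer patients were tested shortly before treatment than was the case.

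**Working it through.** **Inputs.** The Table 3 day ranges and the Appendix 11.1.1 numbering are given above. SAP Table 2 ends its post-start classes for 3, 6, 12 and 24 months at Days 92, 184, 366 and 731. The oral steroid item in Appendix 11.1.2 takes the 3 months before start as 90 days including the start date.

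**Step 1: convert days before start to study days.** A test done n days before start falls on Day 1 - n. Placing each day in the printed ranges:

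| Days before start | Study day | Table 3 class by printed range |
|---|---|---|
| 0 (start day) | 1 | none |
| 1 | 0 | at most 3 months |
| 31 | -30 | at most 3 months |
| 32 | -31 | more than 3; 3 to 6 months |
| 91 | -90 | more than 3; 3 to 6 months |
| 183 | -182 | more than 3; 3 to 6 and 6 to 12 months |
| 184 | -183 | more than 3; 3 to 6 and 6 to 12 months |
| 185 | -184 | more than 3; 6 to 12 months |

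The first class covers 0 - (-30) + 1 = 31 days. Leaving aside the total class beyond 3 months, which is meant to contain the finer ones, Day 1 is the only gap and Days -183 and -182 are the only overlaps.

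**Step 2: see whether any reading of 3 months ends at Day -30.** Taking 3 months as 89 to 92 days before start puts the limit at 1 - 89 = Day -88 to 1 - 92 = Day -91. None gives Day -30. Day -30 is, however, the lower limit of the SAP's own pre-treatment visit window in Appendix 11.1.1, which runs from Day -30 to Day 1.

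**Step 3: find the limits that fit the SAP's scheme.** Day d after start is d - 1 days after Day 1. The same distance before start is Day 1 - (d - 1) = 2 - d.

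- 3 months: 2 - 92 = Day -90
- 6 months: 2 - 184 = Day -182
- 12 months: 2 - 366 = Day -364
- 24 months: 2 - 731 = Day -729

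Table 3 already prints the last two, with the next class starting at -365 and -730. The value -182 also appears, but as the recent end of the 6-to-12-month class, where -183 would fit. Only the 3-month and 6-month boundaries depart from the scheme.

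The oral steroid convention gives a slightly different 3-month limit: 90 days counted back from and including Day 1 end at Day -88, since 1 - (-88) + 1 = 90.

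**Step 4: size.** The misfiled share of pre-start days is (m - 31)/m for a 3-month window of m days before start:

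- m = 89: 58/89 = 65.2%
- m = 90: 59/90 = 65.6%
- m = 91: 60/91 = 65.9%
- m = 92: 61/92 = 66.3%

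These are shares of days. They become shares of tests only if test dates are spread evenly over the window; the documents give no distribution.

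**The case against.** The best defence is that little hangs on this table. It is descriptive and confined to the Xeljanz group. Because label and range conflict, a programmer may have followed the label, in which case nothing is misfiled at the 3-month cut. Both points stand, and they limit the severity. They do not make the printed table right, since a reader cannot tell which of the two was applied.

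A reader might also infer more than the documents support:

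- *That the table misstates compliance with a protocol window for every listed test.* Protocol 7.1 sets the 3-month window only for the tuberculosis check (imaging included) and the three hepatitis B registration tests. For the survey-form tests, including HBV-DNA and HCV antibody, Protocol 7.2 asks for results before treatment and gives no 3-month limit. The SAP describes Table 3 as the status of test implementation and does not call it a compliance measure.
- *That start-day tests are lost.* They lack only a Table 3 timing class. Appendix 11.1.2 separately tabulates chest imaging, tuberculosis and hepatitis tests as performed or not, with no day limits stated. Section 8.2.2 counts post-start tests from Day 2, and the pre-treatment visit window includes Day 1, so printing Day 0 in place of Day 1 looks like a slip. Start-day registration results should also be uncommon, because Protocol 6.4 asks in principle for registration at least a week before treatment.
- *That two thirds of patients would be misreported.* That figure depends on evenly spread test dates and on code that follows the printed ranges.
- *That the infection comparison is biased.* The Table 3 timing classes are not among the covariates in SAP 6.3 and do not enter the definitions of the malignancy, serious-infection or death comparisons in 8.2.3.1.

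**Conclusion.** The error is real and minor. Under the SAP's own day numbering, Table 3 as printed files tests from Day -90 to Day -31 as older than 3 months, taking Day -90 as the 3-month limit. It leaves Day 1 unclassified and assigns Days -183 and -182 twice. On-time testing would be understated. The even-spread figure of 65% to 66% is an illustration of scale, stable across windows of 89 to 92 days, and is not an estimate for this survey. The conclusion assumes that the analysis follows the printed ranges and that the label states what was meant. If the range was meant instead, the month labels of all three adjacent classes are wrong and the table still needs correcting.

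**What to change.** Reconcile the labels and day ranges in Table 3. Following the scheme that the 12- and 24-month cut-points already use:

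- at most 3 months: Day -90 to Day 1
- more than 3 months (total): Day -91 and earlier
- more than 3 and at most 6 months: Day -182 to Day -91
- more than 6 and at most 12 months: Day -364 to Day -183
- all other classes unchanged

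The authors should confirm the 3-month limit against the 90-day convention for oral steroids, which would give Day -88 and move the adjoining limit to Day -89. This concerns the tabulation only and leaves the protocol's testing requirements as they are.

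The sponsor should first check which limits the existing program uses. The cost is a correction to one SAP table and a re-run of one output, with no new data.

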**Table 4. Categories of Tabulation Items for Administration Status**

Item	Category	Note
Daily number of administrations at the first time [time]	Once, twice, $\geq 3$ times	Xeljanz group only
Initial daily dose [mg]	5 mg, 10 mg, $> 10$ mg, other	Xeljanz group only
Duration of administration [day]	Start of treatment - 1 month (Day 1 to Day 31), 1 month < - 3 months (Day 32 to Day 92), 3 months < - 6 months (Day 93 to Day 184), 6 months < - 9 months (Day 185 to Day 275), 9 months < - 12 months (Day 276 to Day 366), 12 months < - 18 months (Day 367 to Day 549), 18 months < - 24 months (Day 550 to Day 731), 24 months < - 30 months (Day 732 to Day 914), 30 months < - 36 months (Day 914 to Day 1096), $> 36$ months (Day 1097-)	Continuous data
Overall administration period [patient-year]	Start of treatment - 1 month (Day 1 to Day 31), 1 month < - 3 months (Day 32 to Day 92), 3 months < - 6 months (Day 93 to Day 184), 6 months < - 9 months (Day 185 to Day 275), 9 months < - 12 months (Day 276 to Day 366), 12 months < - 18 months (Day 367 to Day 549), 18 months < - 24 months (Day 550 to Day 731), 24 months < - 30 months (Day 732 to Day 914), 30 months < - 36 months (Day 914 to Day 1096), $> 36$ months (Day 1097-)	A cumulative value is calculated for each category.
Duration of actual administration [day]	No category	Continuous data Xeljanz group only
Total number of administrations [time]	No category	Continuous data Xeljanz group only

